#### 13.1.3.2 Other Safety Endpoints

Absolute values and changes from Screening/Baseline for clinical laboratory tests, vital signs, and ECGs will be summarized by treatment group for each part of the study using descriptive statistics. Clinical laboratory test, vital sign, CCI [REDACTED] and ECG results that are outside the normal ranges and potentially clinically significant will be flagged and tabulated. The number and percentage of subjects with clinical laboratory test, vital sign, weight/BMI, and ECG parameter values that meet Takeda's predefined criteria for markedly abnormal values at least once postdose will be summarized by treatment and part of the study. Physical examination findings will be listed by subject and treatment group for each part of the study.

### 13.1.4 PK and PD Analysis

Plasma concentrations of TAK-935, its metabolite M-I, and CCI [REDACTED] will be listed for each subject and summarized by each time point for each dose and part of the study.

A population PK/PD analysis approach will be used to determine the population estimates for TAK-935. The PK and PD parameters for TAK-935 will be summarized in a separate population PK/PD report.

### 13.1.5 Secondary and Exploratory Analyses

Safety (clinical laboratory evaluations, vital signs, weight/BMI, and ECGs) and PK (TAK-935) endpoints will be analyzed as the secondary endpoints in the study. CCI [REDACTED]

CCI [REDACTED]

CCI

### **13.2 Interim Analysis and Criteria for Early Termination**

After all subjects have completed the Double-Blind Treatment Period or have discontinued from the study (and prior to completion of the Open-Label Period), an unblinded safety summary may be generated. There will be no early stopping for efficacy or futility.

### **13.3 Determination of Sample Size**

Approximately 20 adult subjects are planned to be randomized. A formal sample size calculation was not performed for this study. The current sample size is deemed appropriate to evaluate the safety and tolerability of TAK-935 before dosing in pediatric subjects <18 years of age. Subjects who fail to complete Part 1 may be replaced and will receive the same treatment as the replaced subject.

## 14.0 QUALITY CONTROL AND QUALITY ASSURANCE

### 14.1 Study-Site Monitoring Visits

Monitoring visits to the study site will be made periodically during the study to ensure that all aspects of the protocol are followed. Source documents will be reviewed for verification of data recorded on the eCRFs. Source documents are defined as original documents, data, and records. The investigator and the study site guarantee access to source documents by the sponsor or its designee (contract research organization) and by the IRB.

All aspects of the study and its documentation will be subject to review by the sponsor or sponsor's designee (as long as blinding is not jeopardized), including but not limited to the Investigator's Binder, study drug, subject medical records, informed consent documentation, documentation of subject authorization to use personal health information (if separate from the informed consent forms), and review of eCRFs and associated source documents. It is important that the investigator and other study personnel are available during the monitoring visits and that sufficient time is devoted to the process.

### 14.2 Protocol Deviations

The investigator should not deviate from the protocol, except where necessary to eliminate an immediate hazard to study subjects. Should other unexpected circumstances arise that will require deviation from protocol-specified procedures, the investigator should consult with the sponsor or designee (and IRB, as required) to determine the appropriate course of action. There will be no exemptions (a prospectively approved deviation) from the inclusion or exclusion criteria.

The site should document all protocol deviations in the subject's source documents. In the event of a significant deviation, the site should notify the sponsor or its designee (and IRB, as required). Significant deviations include, but are not limited to, those that involve fraud or misconduct, increase the health risk to the subject, or confound interpretation of primary study assessment. A Protocol Deviation Form should be completed by the site and signed by the sponsor or designee for any significant deviation from the protocol.

Every attempt will be made to collect each PK and PD blood sample at the designated time point, and the actual time of each blood sample will be recorded on the source document and eCRF.

[Table 14.a](#) defines the target windows for sample collections. Samples collected outside of these collection windows will not be considered a protocol deviation after Day 1 if the time and date of the sample collection is recorded in the eCRF AND the time and date of the dose prior to the sample collection is recorded in the eCRF. The only exception is the Day 1 predose sample, which must be collected prior to dosing on Day 1.

**Table 14.a Windows for PK and PD Blood Sample Collection**

Study Part and Day	Nominal/Target Sampling Time	Window
Part 1, Day 1	Predose (0 hour)	No more than 30 minutes predose
Part 1, Day 1	1, 3 and 5 hours postdose	±15 minutes of nominal time
Part 1, Days 11 and 21	Predose and 1 hour postdose	No more than 30 minutes predose, and ±15 minutes of nominal time, respectively
Part 2, Days 31, 41, and 85	Predose	No more than 30 minutes predose
Part 1, Day 1	Predose (0 hour)	No more than 30 minutes predose

### **14.3 Quality Assurance Audits and Regulatory Agency Inspections**

The study site also may be subject to quality assurance audits by the sponsor or designees. In this circumstance, the sponsor-designated auditor will contact the site in advance to arrange an auditing visit. The auditor may ask to visit the facilities where laboratory samples are collected, where the medication is stored and prepared, and any other facility used during the study. In addition, there is the possibility that this study may be inspected by regulatory agencies, including those of foreign governments (eg, the Food and Drug Administration [FDA], the United Kingdom Medicines and Healthcare products Regulatory Agency, the Pharmaceuticals and Medical Devices Agency of Japan). If the study site is contacted for an inspection by a regulatory body, the sponsor should be notified immediately. The investigator and study site guarantee access for quality assurance auditors to all study documents as described in Section 14.1.

## 15.0 ETHICAL ASPECTS OF THE STUDY

This study will be conducted with the highest respect for the individual participants (ie, subjects) according to the protocol, the ethical principles that have their origin in the Declaration of Helsinki, and the ICH Harmonised Tripartite Guideline for GCP. Each investigator will conduct the study according to applicable local or regional regulatory requirements and align his or her conduct in accordance with the “Responsibilities of the Investigator” that are listed in [Appendix B](#). The principles of Helsinki are addressed through the protocol and through appendices containing requirements for informed consent and investigator responsibilities.

### 15.1 IRB Approval

IRBs must be constituted according to the applicable requirements of each participating region. The sponsor or designee will require documentation noting all names and titles of members who make up the respective IRB. If any member of the IRB has direct participation in this study, written notification regarding his or her abstinence from voting must also be obtained. Those Americas sites unwilling to provide names and titles of all members due to privacy and conflict of interest concerns should instead provide a Federal Wide Assurance Number or comparable number assigned by the Department of Health and Human Services.

The sponsor or designee will supply relevant documents for submission to the respective IRB for the protocol’s review and approval. This protocol, the Investigator’s Brochure, a copy of the informed consent form, and, if applicable, subject recruitment materials and/or advertisements and other documents required by all applicable laws and regulations, must be submitted to a central or local IRB for approval. The IRB’s written approval of the protocol and subject informed consent must be obtained and submitted to the sponsor or designee before commencement of the study (ie, before shipment of the sponsor-supplied drug or study specific screening activity). The IRB approval must refer to the study by exact protocol title, number, and version date; identify versions of other documents (eg, informed consent form) reviewed; and state the approval date. The sponsor will notify the site once the sponsor has confirmed the adequacy of site regulatory documentation and, when applicable, the sponsor has received permission from competent authority to begin the study.

Study sites must adhere to all requirements stipulated by their respective IRB. This may include notification to the IRB regarding protocol amendments, updates to the informed consent form, recruitment materials intended for viewing by subjects, local safety reporting requirements, reports and updates regarding the ongoing review of the study at intervals specified by the respective IRB, and submission of the investigator’s final status report to IRB. All IRB approvals and relevant documentation for these items must be provided to the sponsor or its designee.

Subject incentives should not exert undue influence for participation. Payments to subjects must be approved by the IRB and sponsor.

## 15.2 Subject Information, Informed Consent, and Subject Authorization

Written consent documents will embody the elements of informed consent as described in the Declaration of Helsinki and the ICH Guidelines for GCP and will be in accordance with all applicable laws and regulations. The informed consent form, subject authorization form (if applicable), and subject information sheet (if applicable) describe the planned and permitted uses, transfers, and disclosures of the subject's personal and personal health information for purposes of conducting the study. The informed consent form and the subject information sheet (if applicable) further explain the nature of the study, its objectives, and potential risks and benefits, as well as the date informed consent is given. The informed consent form will detail the requirements of the participant and the fact that he or she is free to withdraw at any time without giving a reason and without prejudice to his or her further medical care.

The investigator is responsible for the preparation, content, and IRB approval of the informed consent form and if applicable, the subject authorization form. The informed consent form, subject authorization form (if applicable), and subject information sheet (if applicable) must be approved by both the IRB and the sponsor prior to use.

The informed consent form, subject authorization form (if applicable), and subject information sheet (if applicable) must be written in a language fully comprehensible to the prospective subject. It is the responsibility of the investigator to explain the detailed elements of the informed consent form, subject authorization form (if applicable), and subject information sheet (if applicable) to the subject. Information should be given in both oral and written form whenever possible and in the manner deemed appropriate by the IRB. In the event the subject is not capable of rendering adequate written informed consent, then the subject's legally acceptable representative may provide such consent for the subject in accordance with applicable laws and regulations.

The subject, or the subject's legally acceptable representative, must be given ample opportunity to: (1) inquire about details of the study and (2) decide whether or not to participate in the study. If the subject, or the subject's legally acceptable representative, determines he or she will participate in the study, then the informed consent form and subject authorization form (if applicable) must be signed and dated by the subject, or the subject's legally acceptable representative, at the time of consent and prior to the subject entering into the study. The subject or the subject's legally acceptable representative should be instructed to sign using their legal names, not nicknames, using blue or black ballpoint ink. The investigator must also sign and date the informed consent form and subject authorization (if applicable) at the time of consent and prior to subject entering into the study; however, the sponsor may allow a designee of the investigator to sign to the extent permitted by applicable law.

Once signed, the original informed consent form, subject authorization form (if applicable), and subject information sheet (if applicable) will be stored in the investigator's site file. The investigator must document the date the subject signs the informed consent in the subject's medical record. Copies of the signed informed consent form, the signed subject authorization form (if applicable), and subject information sheet (if applicable) shall be given to the subject.

All revised informed consent forms must be reviewed and signed by relevant subjects or the relevant subject's legally acceptable representative in the same manner as the original informed consent. The date the revised consent was obtained should be recorded in the subject's medical record, and the subject should receive a copy of the revised informed consent form.

Subjects who consented and provided a PGx sample for DNA (and RNA) analysis can withdraw their consent and request disposal of a stored sample at any time prior to analysis. Notify sponsor of consent withdrawal.

### **15.3 Subject Confidentiality**

The sponsor and designees affirm and uphold the principle of the subject's right to protection against invasion of privacy. Throughout this study, a subject's source data will only be linked to the sponsor's clinical trial database or documentation via a subject ID number. As permitted by all applicable laws and regulations, limited subject attributes, such as sex, age or date of birth, and subject initials may be used to verify the subject and accuracy of the subject's unique ID number.

To comply with ICH Guidelines for GCP and to verify compliance with this protocol, the sponsor requires the investigator to permit the monitor or the sponsor's designee, representatives from any regulatory authority (eg, FDA, Medicines and Healthcare products Regulatory Agency, Pharmaceuticals and Medical Devices Agency), the sponsor's designated auditors, and the appropriate IRBs to review the subject's original medical records (source data or documents), including, but not limited to, laboratory test result reports, ECG reports, admission and discharge summaries for hospital admissions occurring during a subject's study participation, and autopsy reports. Access to a subject's original medical records requires the specific authorization of the subject as part of the informed consent process (see Section 15.2).

Copies of any subject source documents that are provided to the sponsor must have certain personally identifiable information removed (ie, subject name, address, and other identifier fields not collected on the subject's eCRF).

### **15.4 Publication, Disclosure, and Clinical Trial Registration Policy**

#### **15.4.1 Publication and Disclosure**

The investigator is obliged to provide the sponsor with complete test results and all data derived by the investigator from the study. During and after the study, only the sponsor may make study information available to other study investigators or to regulatory agencies, except as required by law or regulation. Except as otherwise allowable in the study site agreement, any public disclosure (including publicly accessible websites) related to the protocol or study results other than study recruitment materials and/or advertisements, is the sole responsibility of the sponsor.

The sponsor may publish any data and information from the study (including data and information generated by the investigator) without the consent of the investigator. Manuscript authorship for any peer-reviewed publication will appropriately reflect contributions to the production and review of the document. All publications and presentations must be prepared in accordance with

this section and the study site agreement. In the event of any discrepancy between the protocol and the study site agreement, the study site agreement will prevail.

#### **15.4.2 Clinical Trial Registration**

In order to ensure that information on clinical trials reaches the public in a timely manner and to comply with applicable laws, regulations, and guidance, Takeda will, at a minimum register all interventional clinical trials it sponsors anywhere in the world on ClinicalTrials.gov and/or other publicly accessible websites before start of study, as defined in Takeda Policy/Standard. Takeda contact information, along with investigator's city, state (for Americas investigators), country, and recruiting status will be registered and available for public viewing.

For some registries, Takeda will assist callers in locating study sites closest to their homes by providing the investigator name, address, and phone number to the callers requesting trial information. Once subjects receive investigator contact information, they may call the site requesting enrollment into the trial. The investigative sites are encouraged to handle the trial inquiries according to their established subject screening process. If the caller asks additional questions beyond the topic of trial enrollment, they should be referred to the sponsor. Any investigator who objects to the sponsor providing this information to callers must provide the sponsor with a written notice requesting that their information not be listed on the registry site.

#### **15.4.3 Clinical Trial Results Disclosure**

Takeda will post the results of clinical trials on ClinicalTrials.gov and/or other publicly accessible websites, as required by Takeda Policy/Standard, applicable laws and/or regulations.

#### **15.5 Insurance and Compensation for Injury**

Each subject in the study must be insured in accordance with the regulations applicable to the site where the subject is participating. If a local underwriter is required, then the sponsor or sponsor's designee will obtain clinical study insurance against the risk of injury to study subjects. Refer to the study site agreement regarding the sponsor's policy on subject compensation and treatment for injury. If the investigator has questions regarding this policy, he or she should contact the sponsor or sponsor's designee.

**Appendix A Schedule of Study Procedures**

	Screening/ Baseline Period (a)	Part 1: Double-Blind Treatment Period (b)			Part 2: Open-Label Treatment Period (b)			Follow-up Period (c)	
Study Day	Days -41 to 0	Day 1	Day 11	Day 21	Day 31	Day 41	Day 85 (c,d)	Day 91	Day 121
Visit Window (days)			±2	±2	±2	±2	±2	±2	±2
Visit Number	1 Screening Visit	2	3	4	5	6	7 Final Visit	8 Follow-up Phone Call	9 Follow-up Visit
Informed consent and assent, if appropriate	X								
Optional PGx informed consent	X								
Inclusion/exclusion criteria	X	X							
Randomization		X							
Demographics, medical history, medication history	X								
Height, weight, BMI	X								
Concurrent medical conditions	X								
Concomitant medications, including AED	X	X	X	X	X	X	X	X	X
Urine drug and alcohol screen (e)	X								
HIV, HBsAg, HCV tests (f)	X								
C-SSRS, if appropriate (g)	X	X					X		
Aberrant behavior checklist	X		X	X	X	X	X		X
FSH and estradiol (h)	X						X		
Serum/urine pregnancy test (i)	X(serum)	X(urine)					X(serum)		
Pregnancy avoidance counseling	X	X	X	X	X	X	X	X	
Vital signs	X	X	X	X	X	X	X		X
Physical examination (j)	X			X			X		

(Footnotes follow table.)

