## 6.0 STUDY DESIGN AND DESCRIPTION

### 6.1 Study Design

This phase 1b/2a, multicenter, randomized, double-blind, placebo-controlled, parallel-group, dose-escalation study with an open-label part is designed to examine the safety, tolerability, PK, and PD of TAK-935 as adjunctive therapy in adult subjects with a diagnosis of developmental and/or epileptic encephalopathies. This study will be conducted at approximately 11 sites in North America with experience in conducting clinical studies in patients with rare epilepsies.

Adult subjects (aged  $\geq 18$  and  $\leq 65$  years) with a diagnosis of developmental and/or epileptic encephalopathies demonstrating bilateral motor seizures (ie, drop seizures, tonic-clonic, tonic, bilateral clonic, atonic, myoclonic-atonic, myoclonic-tonic-clonic, focal seizures with bilateral hyperkinetic motor features) (average of  $\geq 2$  per month during the past 3 months) based on the investigator's assessment will be enrolled. The study will screen a sufficient number of subjects to ensure approximately 20 randomized subjects.

At the Screening Visit (Visit 1), informed consent and/or assent (if applicable) is obtained from the subjects and/or subjects' legally acceptable representative. Subjects will then undergo screening procedures to assess study eligibility in accordance with the study entry criteria (see [Appendix A](#) and Sections 7.1 and 7.2). CCI

The 4-week Baseline Period CCI can begin as soon as informed consent has been signed. At the end of the 4-week Baseline Period and after confirmation of eligibility, subjects will return to the clinic on Day 1 in Part 1 (Visit 2) for randomization. If a subject does not meet the eligibility criteria during the Screening/Baseline Period, the subject will be discontinued from the study (screen failure).

The study will consist of 2 parts:

- Part 1 is a randomized double-blind part consisting of 3 periods: a screening/baseline period (4-6 weeks), titration period (20 days), and maintenance period (10 days). The target final dose of 300 mg BID will be reached after a 20-day titration period.
- Part 2 is an open-label continuation part consisting of 4 periods: a titration period (10 days), maintenance period (44 days), de-escalation period (3-6 days) and follow-up period (30 days).

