### 6.2.3 Endpoints

#### 6.2.3.1 Safety Endpoints

The safety-related endpoints of TEAEs, clinical laboratory test results, vital sign measurements, C-SSRS, and ECG parameters selected for this study are standard methods for assessing safety and tolerability in clinical studies. The ABC-C is a standard tool for measuring the severity of a range of problem behaviors commonly observed in individuals with intellectual and developmental disabilities.

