### **9.3.6 Follow-up Phone Call**

A Follow-up Phone Call will be conducted on Day 91 (Visit 8). All subjects, including those who withdraw early from the study, must complete this Follow-up Phone Call.

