**Footnotes for Appendix A**

(a) The 4-week baseline seizure diary recording can begin as soon as the ICF has been signed. Randomization can occur once the 4-week baseline seizure count of  $\geq 1$  has been obtained and the subject meets all of the inclusion and none of the exclusion criteria.

(b) Three days after each dose up-titration or de-escalation, subjects will be contacted by phone to monitor study drug compliance, concomitant medication use, and AEs.

(c) Subjects who do not enter Part 2 or withdraw early from the study should complete all procedures scheduled for the Final Visit (Visit 7) at time of withdrawal, including dose de-escalation as appropriate, followed by the Follow-up Period (Visits 8 and 9). See Section 6.1 for details.

(d) Dose de-escalation, as appropriate, begins at the Final Visit (ie, if at TAK-935 300 mg BID level, reduce to 200 mg BID for 3 days followed by 100 mg BID for 3 days; if at the 200 mg BID level, reduce to 100 mg BID for 3 days; if at the 100 mg BID level, there is no de-escalation). See Section 6.1 for details.

(e) If urine cannot be collected, the reason should be documented in the source document.

(f) Subjects who are positive for hepatitis C Ab should return to the clinic for an unscheduled visit to provide a blood sample for HCV qPCR.

(g) If the subject is unable to comply with the C-SSRS due to developmental status, a parent proxy may be used for the completion of the C-SSRS. The investigator may also use clinical judgment to assess for suicidal ideation and behavior.

(h) For female subjects only at the Screening and Final Visits.

(i) For female subjects of childbearing potential, a serum pregnancy (hCG) test will be performed at the Screening and Final Visits and a urine pregnancy test will be performed before the morning dose on Day 1 in Part 1 (Visit 2). If urine cannot be collected, the reason should be documented in the source document and the serum pregnancy test obtained at Visit 1 must be confirmed to be negative by the investigator prior to randomization. Additional pregnancy tests may be performed throughout the study at the investigator's discretion.

(j) PE must be captured in the source document. Any clinically significant abnormalities noted prior to administration of study drug should be described and captured on the Medical History form. Any clinically significant changes in PE noted after administration of study drug should be captured on the AE page of the eCRF.

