#### 7.1.1 Definition of Study Day and Baseline

Study day will be calculated relative to the date of the first dosing. Study day prior to the first dose of treatment will be calculated as: date of assessment/event – date of treatment; study day on or after the date of first dose of treatment will be calculated as: date of assessment/event – date of treatment + 1.

Baseline for Part 1 is defined as the last non-missing measurement prior to first dose of study drug in Part 1. Baseline for Part 2 is defined as the last non-missing measurement prior to first dose of study drug.

Baselines for Part 1 and Part 2 (when needed for the analysis) are defined as the last observation prior to the first dose in Part 1 and 2, respectively. Both date and time of the measurement and the dosing date and time should be used when determining the baseline if possible. For Part 1, in the case where the last non-missing measurement (except AE and concomitant medications) and the first dose on Day 1 coincide at the same time, or the same date if time of the measurement is not collected, that measurement will be considered as baseline value for Part 1. For Part 2, in the case where the last non-missing measurement (except AE and concomitant medications) and the first dose on Day 31 coincide at the same time, or the same date if time of the measurement is not collected, that measurement will be considered as baseline value for Part 2.

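### The ABC-C is scheduled at every clinic visit except Day 1, so its scheduled Part 1 baseline is the Screening rating, taken 28 to 42 days before the first dose (minor)

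*Protocol*

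**What the plan says.** **Schedule.** Protocol Appendix A lists "Aberrant behavior checklist" as one row. It is marked at Screening (Visit 1) and on Days 11, 21, 31, 41, 85 and 121. The cells for Day 1 (Visit 2) and Day 91 (Visit 8) are blank. Visit 8 is a telephone contact (Protocol 9.3.6), so Day 1 is the only clinic visit without a rating. The C-SSRS, vital signs, ECG and clinical laboratory tests are marked at both Screening and Day 1.

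**Role.** Protocol 6.2.3.1, under Safety Endpoints, says: "The ABC-C is a standard tool for measuring the severity of a range of problem behaviors". Protocol 9.1.16 describes a caregiver-completed form of 58 items in 5 domains. The scale is not among the primary or secondary endpoints (Protocol 5.2.1 and 5.2.2; SAP 5.1 and 5.2).

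**Timing of Screening.** The Screening/Baseline column of Appendix A runs from Day -41 to Day 0, and Protocol 6.1 gives the period as 4 to 6 weeks. The Appendix A footnotes say: "The 4-week baseline seizure diary recording can begin as soon as the ICF has been signed". Protocol 6.1 continues: "At the end of the 4-week Baseline Period and after confirmation of eligibility, subjects will return to the clinic on Day 1 in Part 1".

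**Baseline rule.** SAP 7.1.1: "Baseline for Part 1 is defined as the last non-missing measurement prior to first dose of study drug in Part 1". The same section adds that the Part 1 and Part 2 baselines "are defined as the last observation prior to the first dose in Part 1 and 2, respectively". The Baseline I window in SAP Table 7.a is Day 1 or earlier, with no limit on how old the value may be.

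**The concern.** Read together, the schedule and the baseline rule leave the ABC-C with a Part 1 reference value that is already 4 to 6 weeks old when dosing starts. Any behavioural change over those weeks is counted as change from baseline at Day 11 and later, although no study drug had been given. Such change is plausible on the protocol's own account: Protocol 4.2 says that epileptic activity may itself contribute to behavioural impairment that can worsen over time.

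The control arm offers limited help. With 16 subjects on TAK-935 and 4 on placebo, readers are likely to look at change within the active arm, which is where pre-treatment drift shows. SAP 7.11 also presents safety endpoints by arm and overall, and pooling arms does not remove a drift that both share.

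**Working it through.** **Step 1: inputs.**
- ABC-C before dosing: Screening only (Appendix A).
- First dose: morning of Day 1 (Protocol 9.3.3).
- Start of the Screening window: Day -41 (Appendix A).
- Shortest screening interval: the 4-week diary, which starts at consent or later (Appendix A footnotes).

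**Step 2: reproduce the plan's figure.**
- Longest gap from Screening to first dose: 1 - (-41) = 42 days = 6.0 weeks.
- Shortest gap: 4 × 7 = 28 days = 4.0 weeks.

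These match the 4 to 6 weeks in Protocol 6.1.

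**Step 3: pre-dose share of the baseline-to-visit interval.** For a visit on Day d, the time since first dose is d - 1 days. With gap g,

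share = g / (g + d - 1).

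| Visit | Days since first dose | Interval from Screening (days) | Pre-dose share, g = 28 | Pre-dose share, g = 42 |
|---|---|---|---|---|
| Day 11 | 10 | 38 to 52 | 28/38 = 74% | 42/52 = 81% |
| Day 21 | 20 | 48 to 62 | 28/48 = 58% | 42/62 = 68% |
| Day 31 | 30 | 58 to 72 | 28/58 = 48% | 42/72 = 58% |
| Day 85, if compared with the Part 1 baseline | 84 | 112 to 126 | 28/112 = 25% | 42/126 = 33% |

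The ±2-day visit window changes little. At Day 9 the share is 28/36 = 78% to 42/50 = 84%. At Day 13 it is 28/40 = 70% to 42/54 = 78%.

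**Step 4: with a pre-dose Day 1 rating.** The gap g falls to 0, the share is 0% at every visit, and the baseline-to-Day 11 interval falls from 38-52 days to 10.

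**Step 5: how well the placebo arm can subtract a common drift.** Assume that all 20 subjects are evaluable and that the standard deviation of change is equal in both arms. The 95% half-width for the difference in mean change is then

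2.10 × √(1/16 + 1/4) = 2.10 × 0.559 ≈ 1.17 SD,

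where 2.10 is the t quantile on 18 degrees of freedom. The subtraction is unbiased but coarse.

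**The case against.** **The ABC-C analysis cannot be seen.** The exploratory objectives, endpoints and analyses are redacted, as are some column headings in the SAP window tables. That the scale is summarised as change from the Part 1 baseline is an inference from the general rule in SAP 7.1.1. This stands, and the conclusion is conditional on it.

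**The randomised comparison is not biased.** The pre-dose interval is common to both arms, and AED regimens are to be stable for at least 4 weeks before Screening and throughout the study. This stands. A reader might infer that the TAK-935 versus placebo result for behaviour is distorted, but the documents do not support that. The cost to the comparison is noise.

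**Other contrasts avoid Screening.** Differences between Days 11, 21, 31, 41, 85 and 121 do not use it, and the Part 2 baseline can be the Day 31 rating. This stands. One sentence in SAP 7.1.1 defines the Part 2 baseline without naming the part whose first dose is meant, but the paragraph after it ties the baseline to the first Part 2 dose.

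**Day 11 is the least favourable visit.** True, so Days 21 and 31 are shown beside it. Share of days is also not a measure of bias. The documents give no ABC-C drift or standard deviation, so the size of any distortion on the scale is unknown.

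**The omission is not unique.** The physical and neurological examinations also have only Screening before dosing. True, but each is done at only three visits, against seven for the ABC-C.

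**The link to earlier psychiatric events is weak.** Protocol 6.2.2.1 reports confusion and acute psychosis in healthy subjects, and a reader might infer that the missing rating would hide such events. The documents do not support that. No ABC-C domain is labelled confusion or psychosis. These events would be captured as AEs, which are collected from consent, assessed on Day 1 and form the primary endpoint.

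**Conclusion.** The scheduling gap is real. Day 1 is the only clinic visit without an ABC-C rating, and SAP 7.1.1 then makes the Screening rating, 28 to 42 days before the first dose, the scheduled Part 1 baseline. An unscheduled pre-dose rating would replace it, but none is planned in the readable text.

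If change from the Part 1 baseline is reported, between about half and four fifths of the elapsed time at the Part 1 ratings and at Day 31 precedes study drug. The effect is drift and noise in within-arm change. No primary or secondary result depends on it.

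This is a design choice with a cheap improvement. It is not a contradiction between the documents, and its severity is minor.

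**What to change.** Mark the ABC-C at Day 1 (Visit 2) in Appendix A, to be completed before the first dose and preferably by the same caregiver who rates later visits. The pre-dose instruction matters: where no time is recorded, SAP 7.1.1 accepts a same-day value as baseline, so a form filled in after dosing could be selected.

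Keep the Screening rating. SAP 7.1.1 then selects the Day 1 value as it stands and falls back to Screening when Day 1 is missing. Having both ratings also allows the pre-treatment drift to be measured in all randomised subjects.

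The cost is one mark in the schedule and one additional 58-item caregiver form per subject, at a visit where subjects already stay for the 5-hour post-dose sample. Eligibility, sample size, dosing and the SAP baseline text do not change.
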